## 14. APPENDICES

Section	Appendix
RAP Section 5 : General Considerations for Data Analyses & Data Handling Conventions	
Section 14.1	Appendix 1: Schedule of Activities 
 
• Protocol Defined Time & Events
 

Section 14.2	Appendix 2: Study Phases and Treatment Emergent Adverse Events 
 
• Treatment Phases for Adverse Events
 
• Treatment Phases for Exacerbations
 

Section 14.3	Appendix 3: Data Handling Conventions 
 
• Baseline Definition & Derivations
 
• Reporting Process & Standards
 

Section 14.4	Appendix 4: Derived and Transformed Data 
 
• General
 
• Study Population
 
• Evaluation of Autoinjector
 
• Safety
 

Section 14.5	Appendix 5: Reporting Standards for Missing Data 
 
• Premature Withdrawals
 
• Handling of Missing Data
 
• Handling of Missing Dates
 

Section 14.6	Appendix 6: Values of Potential Clinical Importance
Other RAP Appendices	
Section 14.7	Appendix 7: Abbreviations & Trade Marks
Section 14.8	Appendix 8: List of Data Displays
Section 14.9	Appendix 9: Example Mock Shells for Data Displays

**14.1. Appendix 1: Schedule of Activities**

## 14.1.1. Protocol Defined Time & Events

	Pre-screening Week -6 to Week -5 a	Screening Week -4 to Week -1	Week 0 (Day 1)	Week 4 (±7 days)	Week 8 (±7 days)	End of Study/ Early Withdrawal b Week 12 (±7 days)
Visit number	V0	V1	V2	V3	V4	V5
Informed consent	X					
Demography/child bearing status assessment	X					
Medical history		X				
Asthma and Exacerbation history	X					
Asthma Therapy history	X					
Smoking history		X				
Parasitic screening c		X				
Prior needle use / self-administration assessment		X				
Inclusion/Exclusion criteria		X				
Training session			X d			
Autoinjector self-administration in clinic			X		X	
Autoinjector self-administration outside of clinic				X e, f		
Laboratory:						
Urine pregnancy test		X	X d	X d	X d	X
Haematology (including eosinophils) g / Clinical Chemistry		X	X d	X d	X d	X d
Urinalysis		X				
Immunogenicity			X d			X d
PK			X d	X d	X d	X d
Pharmacogenetics h			X			
Physical/Clinical:						
Vital signs i		X	X d	X d	X d	X
12-lead ECG		X				X
Physical examination		X				X
Weight		X				

CONFIDENTIAL

204959

	Pre-screening Week -6 to Week -5 a	Screening Week -4 to Week -1	Week 0 (Day 1)	Week 4 (±7 days)	Week 8 (±7 days)	End of Study/ Early Withdrawal b Week 12 (±7 days)
Visit number	V0	V1	V2	V3	V4	V5
Concomitant Medication	X	X	X	X	X	X
Asthma Exacerbations		X	X	X	X	X
Serious Adverse Events j,k,l	X	X	X	X	X	X
Adverse Events j,k,l			X	X	X	X
Dispense patient diary			X m	X	X	
Return/review patient diary				X	X	X n
Dispense autoinjector for self-administration outside of clinic				X		
Return/ inspect autoinjector following self-administration outside of clinic					X	X n,o
Subject completed pain assessment diary (0, 1- and 24hours post dose)			X	X f	X	
Autoinjector observer assessment checklist			X		X	
Subject/caregiver completed autoinjector checklist				X f		
Assessment of injection success			X		X p	
Device usability/functionality questionnaire						X
Exit Interview q						(X)

- a. Pre-screening Visit (V0) can occur on the same day as the Screening Visit (V1) but must be completed prior to initiating any Visit 1 procedures; The Pre-screening Visit can be conducted up to a maximum of 2 weeks prior to the Screening Visit.
- b. The Early Withdrawal Visit will occur 4 weeks (±7 days) after last dose of mepolizumab for any subject who withdraws prior to Week 12
- c. Parasitic screening is only required in countries with high-risk or for subjects who have visited high-risk countries in the past 6 months. Sites should use local laboratories.
- d. Perform prior to mepolizumab administration during the study and prior to restarting pre-study mepolizumab treatment on study completion/early withdrawal.
- e. Subjects will be instructed to contact clinical study staff at any time if they have concerns or questions regarding self-administration. They will have the option of returning to the clinical site for further training or assistance with self-administration. Requirement for additional training or assistance will be documented.
- f. Self-administration of mepolizumab using the autoinjector should occur within 24 hours following the clinic visit.
- g. Includes measurement of eosinophil levels for pharmacodynamic analysis at Visits 2, 3, 4 and 5 (Week 0, 4, 8 and 12)
- h. Pharmacogenetic sample may be drawn any time after the respective informed consent form is signed and the subject is enrolled.
- i. Vital signs include temperature, sitting blood pressure, respiratory rate and pulse.

**CONFIDENTIAL**

204959

- j. Any SAEs assessed as related to study participation (e.g., study treatment, protocol-mandated procedures, invasive tests, or change in existing therapy) or related to a GSK concomitant medication, will be recorded from the time a subject consents to participate in the study up to and including any follow up contact. All other AEs/SAEs are recorded from the start of study treatment until the End of Study / Early Withdrawal visit.
- k. Injection site reactions (e.g., induration, erythema, edema, rash, pruritus, pain) are to be recorded on both AE and SAE CRF forms.
- l. Information on systemic reactions and events that meet the anaphylaxis criteria is collected on both AE and SAE CRF forms.
- m. Patient diary should be dispensed prior to administration of injection
- n. For any subject who withdraws prior to Week 12 (V5), patient diary and study drug for self-administration outside of clinic will be returned at the Early Withdrawal visit (if applicable).
- o. Assessment to be completed at the Early Withdrawal visit only if the dose of mepolizumab immediately prior to withdrawal was administered outside of the clinic.
- p. Includes both the injection outside the clinic from Week 4 (V3) and the injection in clinic at Week 8 (V4)
- q. In a subset of subjects only. Completed over the telephone after the End of Study/Early Withdrawal Visit

## 14.2. Appendix 2: Study Phases and Treatment Emergent Adverse Events

### 14.2.1. Treatment Phases

Assessments and events will be classified according to the time of occurrence relative to the first dose of study treatment.

#### 14.2.1.1. Treatment Phases for Adverse Events

Treatment State	Definition
Pre-Treatment	
 
AE start date < First dose of study treatment
 

On-Treatment	
 
First dose of study treatment ≤ AE start date ≤ Last dose of study treatment + 28 days
 
Any AE with missing start date will be assumed to be “On-Treatment”.
 
Any AE with partial start date will be assumed to be “On-Treatment” unless there is evidence to the contrary (e.g. month/year of onset is present and is earlier than the month/year of the first dose of study treatment).
 

Post-Treatment	
 
AE start date > Last dose of study treatment + 28 days
 

Note: the first dose of study treatment will be defined as the earliest dosing date/time entered into the eCRF, regardless of whether self-administration of the injection was successful i.e. full dose administered for this dosing occasion.

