## 4.2. Treatment Arms and Duration

This is a single arm study in which all subjects will receive mepolizumab 100 mg SC every 4 weeks, using the liquid drug product in autoinjector presentation, for 12 weeks. Each subject will participate in the study for up to 18 weeks (Visit 0 to the End of Study Visit (Visit 5) as described in Table 1.

Phase	Phase Title	Duration	Description
1	Pre-screening	0 to 2 weeks	At the Pre-screening Visit (Visit 0), details about the study and procedures will be explained through the informed consent process. The Pre-screening Visit can occur on the same day as the Screening Visit (Visit 1) but must be completed prior to initiating any Visit 1 procedures.
2	Screening	1 to 4 weeks	Subjects will be assessed for eligibility at the Screening Visit (Visit 1). Blood draws will be taken for assessments of liver function and to determine blood eosinophil levels in subjects not previously using mepolizumab and who do not meet the historical blood eosinophil criterion.
3	Treatment	12 weeks	At Visit 2 (Week 0) those subjects who continue to meet the eligibility criteria and the continuation to treatment criteria (see Section 5.3) will receive mepolizumab 100 mg SC every 4 weeks for a total of 3 doses. The treatment period will conclude with subjects completing End of Study Visit (Visit 5) assessments approximately 4 weeks after the subject was administered their last dose of study treatment at Visit 4.

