### Females:

A female subject is eligible to participate if she is not pregnant (as confirmed by a negative urine human chorionic gonadotrophin (hCG) test), not planning to become pregnant during the time of study participation (and up to 16 weeks after the last dose), not lactating, and at least one of the following conditions applies:

a. Non-reproductive potential defined as:

• Pre-menopausal females with one of the following:

- Documented tubal ligation
- Documented hysteroscopic tubal occlusion procedure with follow-up confirmation of bilateral tubal occlusion
- Hysterectomy
- Documented Bilateral Oophorectomy
- Postmenopausal female (see Appendix 3 for specific criteria).
- b. Reproductive potential and agrees to follow one of the options listed in the Modified List of Highly Effective Methods for Avoiding Pregnancy in Females of Reproductive Potential (FRP) (see Appendix 3) from 30 days prior to the first dose of study medication and until 16 weeks after the last dose of study medication and completion of the End of Study/Early Withdrawal visit.

The investigator is responsible for ensuring that subjects understand how to properly use these methods of contraception.

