#### 204959

## 7.1. Time and Events Table

		Pre-screening Week -6 to Week - 5ª	Screening Week -4 to Week - 1	Week 0 (Day 1)	Week 4 (±7 days)	Week 8 (±7 days)	Week 12 (±7 days)
		v					Early Withdrawal b
Procedures	Visit number	V0	V1	V2	V3	V4	V5
Informed consent		Х					
Demography/child bearing status asso	essment	Х					
Medical history			Х				
Asthma and Exacerbation history		Х					
Asthma Therapy history		Х					
Smoking history			Х				
Parasitic screening c			Х				
Prior needle use / self-administration	assessment		Х				
Inclusion/Exclusion criteria			Х				
Training session				Xď			
Autoinjector self-administration in clinic				Х		Х	
Autoinjector self-administration outsid	e of clinic				X e, f		
Laboratory:							
Urine pregnancy test			Х	Xď	Xď	Xď	Х
Hematology (including eosinophils) g /	Clinical Chemistry		Х	Xď	Xď	Xď	Xď
Urinalysis			Х				
Immunogenicity				Xď			Xď
PK				Xď	Xď	Xď	Xď
Pharmacogenetics h				Х			
Physical/Clinical:							
Vital signs i			Х	Xq	Xď	Xď	Х
12-lead ECG			Х				Х
Physical examination			Х				Х
Weight			Х				
Concomitant Medication		Х	Х	Х	Х	Х	Х
Asthma Exacerbations			Х	Х	Х	Х	Х
Serious Adverse Events j,k,l		Х	Х	Х	Х	Х	Х
Adverse Events j,k,l				Х	Х	Х	Х

	Pre-screening Week -6 to Week -	Screening Week -4 to Week -	Week 0 (Day 1)	Week 4 (±7 days)	Week 8 (±7 days)	Week 12 (±7 days)
	5	1	,			End of Study/ Early Withdrawal b
Procedures Visit number	VO	V1	V2	V3	V4	V5
Dispense patient diary			Xm	Х	Х	
Return/review patient diary				Х	Х	Xn
Dispense autoinjector for self-administration outside of clinic				Х		
Return/ inspect autoinjector following self-administration					Х	X n,o
outside of clinic						
Subject completed pain assessment diary (0, 1- and 24-			Х	Xf	Х	
hours post dose)						
Autoinjector observer assessment checklist			Х		Х	
Subject/caregiver completed autoinjector checklist				Xf		
Assessment of injection success			Х		Xp	
Device usability/functionality questionnaire						Х
Exit Interview Q						(X)

a. Pre-screening Visit can occur on the same day as the Screening Visit but must be completed prior to initiating any Visit 1 procedures; The Pre-screening Visit can be conducted up to a maximum of 2 weeks prior to the Screening Visit.

- b. The Early Withdrawal Visit will occur 4 weeks (±7 days) after last dose of mepolizumab for any subject who withdraws prior to Week 12

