### 2.3. Study Design

Overview of Study Design and Key Features	

The diagram illustrates the study timeline. It begins with Pre-screening (0 to 2 weeks) and Screening (1 to 4 weeks). Key visits are marked: Visit 0 (Pre-screen), Visit 1 (Screen), and Visit 2 (Start of Study). Mepolizumab administration is shown as a series of doses: the first dose is administered in-clinic at Visit 2 (Week 0), the second dose is self-administered out-of-clinic at Visit 3 (Week 4), and the third dose is administered in-clinic at Visit 4 (Week 8). The study concludes at the End of Study (Week 12). A legend indicates that blue triangles represent 'In Clinic' and yellow triangles represent 'Out of Clinic'.
	

Design Features
	
 
• 12-week treatment period, open-label, single arm, repeat-dose, multi-centre study in subjects with severe eosinophilic asthma.
 
• Subjects (or their caregiver, if applicable) will be trained to administer mepolizumab liquid drug product in autoinjector prior to the first dose (Visit 2).
 
• Each autoinjector will have labelling that includes a pictogram plus standard labelling elements, or a standard labelling without the pictogram dependant on the country in which it is being used.
 
• Mepolizumab will be self-administered (by subject or caregiver, if appropriate) under observation in the clinic for first dose (Visit 2) and third dose (Visit 4). The second dose of mepolizumab will be self-administered (by subject or caregiver, if appropriate) at home without observation following Visit 3.
 
• All injections will be assessed by the investigator for success based on             
 
○ Direct observation of the self-administration if the dose was administered in the clinic, and inspection of the autoinjector.
 
○ Subject/caregiver completed checklist if the dose was administered outside the clinic, and inspection of the returned autoinjector.
 
 
 

Main Subject Entry Criteria
	
 
• Subjects aged 12 or older with physician diagnosis of asthma for <math>\geq 2</math> years.
 
 
Either
 
 
• Subjects receiving 100mg subcutaneous (SC) mepolizumab for the treatment of severe eosinophilic asthma every 4 weeks for at least 12 weeks prior to the study.
 

Overview of Study Design and Key Features	

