## 10. EXACERBATIONS

Analyses of exacerbations will be based on the “All Subjects (Safety)” population. The number and percentage of subjects with at least one on-treatment exacerbation will be summarised. On-treatment exacerbations are defined in Section [14.2.1.2](#). All exacerbation data will be listed.

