#### 14.2.1.2. Treatment Phases for Exacerbations

Treatment State	Definition
Pre-Treatment	
 
Exacerbation onset date < First dose of study treatment
 

On-Treatment	
 
First dose of study treatment ≤ exacerbation onset date ≤ Last dose of study treatment + 28 days
 
Any exacerbation with missing onset date will be assumed to be “On-Treatment”.
 
Any exacerbation with partial onset date will be assumed to be “On-Treatment” unless there is evidence to the contrary (e.g. month/year of onset is present and is earlier than the month/year of the first dose of study treatment).
 

Post-Treatment	
 
Exacerbation onset date > Last dose of study treatment + 28 days
 

Note: the first dose of study treatment will be defined as the earliest dosing date/time entered into the eCRF, regardless of whether self-administration of the injection was successful i.e. full dose administered for this dosing occasion.

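### The on-treatment phase stops 28 days after the last dose although Visit 5, which closes the treatment period, may fall later, so some collected exacerbations and special-interest events miss their only summary tables.

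*SAP*

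**What the plan says.** **Cut-off.** SAP 14.2.1.1 counts an adverse event as on-treatment from the first dose as long as "AE start date ≤ Last dose of study treatment + 28 days". SAP 14.2.1.2 uses the same limit for exacerbations: "exacerbation onset date ≤ Last dose of study treatment + 28 days". Anything later is post-treatment.

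**Final visit.** Protocol 4.2 (Table 1) has the treatment period conclude with the Visit 5 assessments, "approximately 4 weeks after the subject was administered their last dose of study treatment at Visit 4". The Time and Events Table (Protocol 7.1) gives both Week 8 and Week 12 a ±7-day window. Footnote b sets the same tolerance for withdrawals: "The Early Withdrawal Visit will occur 4 weeks (±7 days) after last dose of mepolizumab".

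**Collection.** SAP 14.1.1, footnote j: "All other AEs/SAEs are recorded from the start of study treatment until the End of Study / Early Withdrawal visit". Protocol 7.8 has exacerbations assessed at every study visit, and the Time and Events Table includes Visit 5.

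**Displays.** SAP 10: "The number and percentage of subjects with at least one on-treatment exacerbation will be summarised". The only exacerbation table is 10.1. The special-interest summary and profile tables (11.20 to 11.37) are all titled on-treatment. SAP 2.2, however, defines the exacerbation endpoint as the number of subjects with at least one exacerbation, without naming a phase. SAP 2.1 reports no change to the protocol's analysis plan other than one added population.

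**The concern.** The 28-day tail equals one dosing interval with no allowance for the visit window. Whenever Visit 5 takes place after day 28, an interval opens in which events are still collected, and which the protocol still treats as part of the treatment period, but which the SAP labels post-treatment.

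Exacerbations are affected most directly. An exacerbation on day 30, before a permitted Visit 5 on day 32, meets the endpoint as SAP 2.2 words it but is absent from the only table that reports that endpoint. Special-interest events that need not cluster near dosing (delayed systemic reactions, infections, malignancies, serious cardiovascular events) are affected in the same way. With about 158 subjects and infrequent events, one or two reclassified cases could visibly change a reported count.

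The SAP also treats neighbouring data differently. Visit 5 laboratory and ECG values enter the Week 12 tables by planned time (SAP 14.3.2) even when taken on day 30. An AE with no start date is counted as on-treatment on worst-case grounds (SAP 14.5.3), while one correctly dated to day 29 is not.

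**Working it through.** **1. Reproduce the plan's own figure.** SAP 2.3 describes a "12-week treatment period, open-label, single arm, repeat-dose, multi-centre study". Nominal last dose at Week 8 = 56 days after first dose; 56 + 28 = 84 days = 12 weeks. On nominal dates the cut and the treatment period end together, so the gap comes only from the visit windows.

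**2. Interval from last dose to Visit 5.** The documents do not state the anchor of the Visit 5 window, so both readings are shown.
- A, Visit 5 timed from the last dose: 28 ± 7 gives 21 to 35 days.
- B, both windows counted from Day 1: shortest 77 − 63 = 14 days, longest 91 − 49 = 42 days.

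Protocol 4.2 and the synopsis time Visit 5 from the last dose, which favours A. Early Withdrawal is 21 to 35 days under either reading.

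**3. Share of final visits after day 28.** The documents give no visit-date distribution. Assumption: whole days, uniform in the window. Day 28 itself counts as on-treatment.
- A: 7 of 15 days = 46.7%.
- B: (14 + 13 + … + 1)/225 = 105/225 = 46.7%; beyond day 35, 28/225 = 12.4%.
- Sensitivity under A: 33% if the actual spread is ±1 day, 43% if ±3 days, 87.5% if visits are uniform from day 28 to day 35.

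**4. Follow-up beyond the cut, per subject.**
- A: (1 + 2 + … + 7)/15 = 28/15 = 1.87 days; 1.87/84 = 2.2%; maximum 7 days.
- B: Σ d(15 − d)/225 for d = 1 to 14 = 560/225 = 2.49 days; 2.49/84 = 3.0%; maximum 14 days.

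Over the 150 planned completers: 150 × 28/15 = 280 person-days (A) or 150 × 560/225 = 373 person-days (B), that is 0.77 or 1.02 person-years.

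**5. What that could mean in exacerbations.** The documents give no expected rate. If it were 0.5 to 1.5 per person-year (an assumption), the excluded time would hold 0.77 × 0.5 = 0.4 to 1.02 × 1.5 = 1.5 exacerbations in the whole study.

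**6. Where a late event still appears.**

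| Event starting after day 28 | Left out of | Still shown in |
|---|---|---|
| Exacerbation | Table 10.1 | Listing 21 |
| Special-interest AE | Tables 11.20–11.37 | Table 11.2, Listings 28–35 with phase flag |
| Special-interest SAE | Tables 11.20–11.37 | Tables 11.2 and 11.17, listings |

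**The case against.** A tail of one dosing interval is an accepted convention. It matches the exposure formula in SAP 14.4.2 (last dose − first dose + 29 days), and every later event is still reported somewhere. Besides Tables 11.2 and 11.17, the titles of Tables 11.6, 11.7, 11.9 and 11.19 (drug-related events and discontinuations) carry no phase limit. Exacerbation is an other endpoint, the protocol says efficacy is not being assessed, and there is no comparator to bias. A window that ends at the visit would vary in length between subjects. All of this bears on the size of the problem, and most of it stands. The last point has limited force: collection already stops at the visit, so under the present rule a subject seen on day 21 is observed for less time than one seen on day 28.

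The objection about restarting treatment also stands. Protocol 4.2 and Time and Events footnote d let pre-study mepolizumab resume once the final assessments are done, with no bar on the same day, and phases are assigned by date. A longer window could therefore take in a reaction to a non-study dose given on the visit date. The present rule has the same weakness when Visit 5 falls on or before day 28.

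A reader might infer several stronger points that the documents do not support:
- *That nearly half of subjects would have findings excluded.* The 46.7% counts late visits under an assumed distribution, not events.
- *That Visit 5 laboratory or ECG findings leave the special-interest tables.* Most such findings are not special-interest events as SAP 11.1.1 lists them. As ordinary AEs they move from Table 11.1 to Table 11.2, and the values themselves are summarised by visit.
- *That injection-site reactions are undercounted.* This would need onset more than 28 days after the last injection, which is unlikely.
- *That the protocol regards exposure as relevant for 16 weeks.* The phrase "until 16 weeks after the last dose of study medication and completion of the End of Study/Early Withdrawal visit" belongs to the contraception requirement, and the same period is used for pregnancy reporting. Neither concerns attribution of AEs.

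**Conclusion.** The point holds, with a small effect. The 28-day cut is narrower than the treatment period in Protocol 4.2 and the collection period, and Table 10.1 is narrower than the endpoint it reports. Tables 11.20 to 11.37 share the gap. Only events starting after day 28 and on or before the final visit are affected.

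The gap is at most 7 days per subject if Visit 5 is timed from the last dose. The 14-day maximum applies only if both windows run from Day 1, which the documents do not say. The averages of 1.9 and 2.5 days rest on uniform visit timing; consistently late visits would raise them (3.5 days if uniform from day 28 to day 35) and tighter scheduling would lower them (0.3 days at ±1 day). The primary endpoint is untouched. The change is worth making because it aligns a named endpoint with its table and needs no new data.

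**What to change.** **Table 10.1 (SAP 10 and 14.2.1.2).** Count exacerbations from first dose to the later of last dose + 28 days and the End of Study/Early Withdrawal visit date.

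**Tables 11.20 to 11.37 (SAP 14.2.1.1 and Appendix 8).** Either use the same window, or keep the 28-day cut and add a post-treatment row to each table.

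**Restarted treatment.** Under either rule, exclude or flag events that start after pre-study mepolizumab is resumed, including on the visit date. Where onset time is missing and the order cannot be established, flag the event rather than exclude it.

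**Cost.** A few lines of SAP wording and some table programming, with no new data collection. Counts may be slightly higher, and a window that runs to the visit will differ slightly from the exposure duration in SAP 14.4.2; a footnote on the affected tables would explain this.
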